## 18. Version History

---

Version	Summary of Changes	Author(s)/Title
[REDACTED]	[REDACTED]	[REDACTED]

	
[Redacted text]
	
[Redacted text]

--	------------------------	------------------------

# Vectors Post Market Clinical Investigation Plan

#MDT17053

Version 4.0 08 May 2018

Page 76 of 80

[Redacted]
	
[Redacted]
	
[Redacted]
	
[Redacted]

-------------------	-------------------	-------------------	-------------------

# Vectors Post Market Clinical Investigation Plan

#MDT17053

Version 4.0 08 May 2018

Page 80 of 80

	

█

█

█

	
[Redacted content]
	
--	---	---------------------------	--

NANS	North American Neuromodulation Society
NPU	Neuro Programmer Upload
ODI	Oswestry Disability Index
PGIC	Patient Global Impression of Change
PM	Post-Market
PT	Preferred Term (classification within MedDRA)
SAP	Statistical Analysis Plan
SCS	Spinal Cord Stimulation
SOC	System Organ Class (classification within MedDRA)
SSA	Subject Satisfaction Assessment
UK	United Kingdom
US	United States
USADE	Unanticipated Serious Adverse Device Effect
VAS	Visual Analog Scale

3. Introduction

The Vectors Post Market (PM) study is a global, prospective, single-arm, multi-center, open label study evaluating the efficacy of spinal cord stimulation (SCS) therapy for pain relief using high dose (HD) stimulation parameters while targeting a specific anatomical location.

The purpose of this Statistical Analysis Plan (SAP) is to provide detailed descriptions of the planned analyses of the objectives listed in the study Clinical Investigation Plan (CIP). This SAP is comprehensive of the statistical methods and analyses to be included in the final study report. Unless otherwise specified, all analyses listed within this SAP will be included in the final study report.

4. Study Objectives

4.1. Primary Objective

To demonstrate a significant improvement in overall (low back and leg) pain intensity using HD stimulation starting at 90 - 200 μ sec and 1000 Hz with lead placement spanning the T9/T10 disc space, as measured by the Visual Analog Scale (VAS), from Baseline to the 3-Month Visit.

4.2. Safety Assessment

This study will characterize all device-, therapy-, or procedure-related adverse events and device deficiencies from enrollment to study exit.

4.3. Secondary Objectives

1. To characterize the overall (low back and leg) pain efficacy responder rate, as measured by the VAS, from Baseline to the 3-Month Visit, with a confidence interval within $\pm 10\%$
2. To characterize the low back pain efficacy responder rate, as measured by the VAS, from Baseline to the 3-Month Visit, with a confidence interval within $\pm 10\%$
3. To characterize the leg pain efficacy responder rate, as measured by the VAS, from Baseline to the 3-Month Visit, with a confidence interval within $\pm 10\%$

[REDACTED]

5. Investigation Plan

[figure not shown]
This is a global, prospective, single-arm, multi-center, open label study evaluating the efficacy of SCS therapy for pain relief using HD stimulation parameters while targeting a specific anatomical location. The study will be conducted at up to 30 centers globally.

To be enrolled in the study, adult patients must have both low back and leg pain of at least 50mm (out of 100mm) on the Visual Analog Scale (VAS), and an Oswestry Disability Index (ODI) score from 21 to 80 (out of 100). They must be on stable pain medications for the treatment of their pain and be willing to not increase these medications through the 3-Month Visit.

Subjects who meet the inclusion and exclusion criteria at Baseline undergo a trial lead implant procedure. At Device Trial, if the final lead placement after paresthesia mapping spans the T9/T10 disc space, the subjects may continue in the study. Subjects using HD stimulation settings with a self-reported pain improvement of at least 50% at Day 2 or Day 4 of the trial are then eligible to receive a permanent SCS implant within the study.

Once implanted with a permanent SCS system, if the final lead placement spans the T9/T10 disc space, the subject continues in the study with the following visits: Device Activation, 2-Week, 4-Week, 6-Week, 3-Month (Primary and Secondary objectives visit), 6-Month, and 12-Month, with a planned phone call between each visit. Subjects will discontinue from the study following the 12-Month Visit. Figure 1 shows the study visits from Baseline through the 12-Month Visit.

Figure 1. Vectors PM study visit flowchart

6. Determination of Sample Size

The sample size for this study has been determined by the secondary objectives, which are to characterize a responder rate with a confidence interval within $\pm 10\%$. Calculations were performed using PASS11, Confidence Intervals for One Proportion, with Confidence Level = 0.95, P = 0.5, Confidence Interval Formula = Score (Wilson), Interval Type = Two-Sided. Table 1 shows the 95% confidence interval for a 50% responder rate for 50-100 subjects. A sample size of 100 subjects provides a 95% confidence interval within 9.6% of the responder rate estimate, if the observed responder rate is 50%. The confidence interval is the widest with a responder rate of 50%; a lower or higher responder rate will have a narrower confidence interval.

Table 1. 95% Confidence Interval (CI) for Responder Rate = 50%

N	Lower Limit	Upper Limit	CI Width	+/- Range
50	36.6%	63.4%	26.7%	13.4%
60	37.7%	62.3%	24.5%	12.3%
70	38.6%	61.4%	22.8%	11.4%
80	39.3%	60.7%	21.4%	10.7%
90	39.9%	60.1%	20.2%	10.1%
100	40.4%	59.6%	19.2%	9.6%

Calculations using PASS11 show a required sample size of 26 subjects for the primary objective: Tests for One Mean, alpha = 0.05, power = 0.9, null mean (Mean0) = 0, alternative mean (Mean1) = 20, standard deviation = 30, alternative hypothesis = Mean0 \neq Mean1, and Infinite population size. A sample size of 100 subjects derived for the secondary objectives ensures over 99% power under these same assumptions.

7. Statistical Methods

7.1. Study Subjects

7.1.1. Disposition of Subjects

Subject disposition will be summarized by site and overall in a table showing the number of subjects at these visits: Baseline, Trial Day 0, Implant, Activation, 3-Month, 6-Month, and 12-Month. Additionally, the subject disposition at each visit will be depicted in a flow diagram. For subjects within the Trialed Analysis Set (see section 7.1.3), the number who report at least a 50% improvement in pain at the Trial Day 2, Day 4, and Day 6 Visit will be summarized.

7.1.2. Clinical Investigation Plan (CIP) Deviations

Protocol deviations will be summarized by deviation type and associated visit. A listing of protocol deviations, which will include the reason for the deviation and any other additional details about the deviation, will also be included in the final study report.

7.1.3. Analysis Sets

There will be 4 population sets for the purposes of analysis in this study.

Enrolled Analysis Set: All consented subjects.

Trialed Analysis Set: All subjects who have a Device Trial Day 0 Visit.

Implanted Analysis Set: All subjects who have a positive device trial with HD parameters at T9/T10 and are implanted with a neurostimulation system.

Treated Analysis Set: All subjects in the Implanted Analysis Set whose devices are activated at the Device Activation Visit.

7.2. General Methodology

Summary statistics will be presented for continuous measures (N, means, medians, standard deviations, minimums and maximums) and categorical measures (N, percent, frequency distributions) with two-sided 95% confidence intervals as appropriate. Tests of change from baseline will use the one-sample paired t-test. The score (Wilson) method will be used to calculate the 95% confidence intervals of responder rates and percentages of subjects.

All analyses will be pooled by neurostimulator model unless otherwise specified.

7.3. Center Pooling

[figure not shown]
Data will be pooled across centers for all analyses. No single site may implant more than 25 subjects. This is intended to reduce the possibility that a site with atypical results will be overly influential in the study results based on pooled data.

Summary statistics of the primary, secondary, and safety assessments will be reviewed by center. This analysis will not be included in the final clinical study report unless there is high variability in results across centers.

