### 13.1.4. Center pooling

All investigators in the proposed study will conduct the study according to a common protocol and utilize the same CRFs to collect study data. In addition, site study personnel training will be conducted prior to initiation of the study in each site and periodic monitoring will be conducted by Medtronic to ensure compliance with protocol requirements.

Data will be pooled across centers for all analyses. No single site will be allowed to implant more than 25 subjects. This is intended to reduce the possibility that a site with atypical results will be overly influential in the study results based on pooled data.

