7.4. Handling of Missing, Unused, and Spurious Data and Dropouts

All available data will be included in the data listings and tabulations.

Imputation of values for missing pain scores for primary and secondary efficacy analyses will be performed as follows. For scheduled follow-up visits with missing VAS pain scores, if an Unscheduled Visit occurred within the scheduled visit window, and the VAS pain scores were collected at that Unscheduled Visit, the VAS pain scores from the Unscheduled Visit will be used in the analyses of that scheduled visit. Otherwise, the missing VAS pain scores will be imputed using multiple imputations (MI).

Following imputation, the objectives will be evaluated using MI analysis methods.

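### Does SAP 7.3 need a definition of high variability before by-center results can be left out of the final report?

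*SAP*

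**What the plan says.** Three statements in the plan bear on this point.

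- **Pooling.** Protocol 13.1.4 states: "Data will be pooled across centers for all analyses". SAP 7.3 repeats it. Both add a ceiling of 25 implanted subjects per site, meant to keep one unusual site from dominating the pooled result.
- **Center review.** SAP 7.3 goes on: "Summary statistics of the primary, secondary, and safety assessments will be reviewed by center". It then adds: "This analysis will not be included in the final clinical study report unless there is high variability in results across centers".
- **Reporting default.** The SAP introduction (section 3) states: "Unless otherwise specified, all analyses listed within this SAP will be included in the final study report".

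No readable part of either document gives a measure, a threshold or a decision-maker for high variability. Protocol 13.1.6 (Reports) and parts of SAP 7.9 are redacted, so a definition there cannot be ruled out, and its absence from the public text is not held against the plan.

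**The concern.** A rule that shows a table only if the table looks a certain way invites the question of who decides, and by what standard. Here the by-center results are themselves the input to the decision, so the choice is necessarily made after seeing them. Protocol section 6 lists limiting center bias, and an SAP written before the data are analyzed, among its protections. SAP 7.1.1 promises disposition by site, but no readable section promises efficacy or safety by site unconditionally.

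The stake is what a reader can learn about consistency across centers. Without a by-center table, the reader knows that the review did not judge the spread high, but not what standard was used. If centers are small, chance alone produces a wide spread, and two careful analysts could classify the same data differently.

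**Working it through.** **The plan's own figures.** SAP section 6 uses "alternative mean (Mean1) = 20, standard deviation = 30" with two-sided alpha 0.05 and power 0.90.

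- At n = 26 the noncentrality is (20/30) × √26 = 3.40, and the t-test power is 0.904, so 26 is reproduced. At n = 100 the power exceeds 0.9999.
- The Wilson interval for 50 of 100 is 40.4% to 59.6%, a half-width of 9.6 points, as in SAP Table 1.

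No stated figure is in dispute.

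**Site sizes.** SAP section 5 says: "The study will be conducted at up to 30 centers globally". With about 100 analyzed subjects, an even spread gives 100/30 = 3.3 per site. At the other end, the ceiling of 25 allows 100/25 = 4 full sites. Protocol section 6 encourages 8 enrolled per site, with no minimum. The equal-sized layouts below are assumptions chosen to cover that range.

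**Chance spread with no true center differences.** Site responder counts are binomial(m, 0.5), with 200,000 simulated trials per layout. For the primary endpoint, the expected lowest and highest site means are 20 ± e × 30/√m, where e is the expected largest of k standard normal values (2.043, 1.965, 1.629 and 1.029 for k = 30, 25, 12 and 4). For example, 25 sites of 4 give 20 ± 1.965 × 15 = -9.5 and 49.5 mm.

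| Layout (sites × subjects) | Mean lowest and highest site rate | Mean lowest and highest site change (mm) |
|---|---|---|
| 30 × 3 | 1% and 99% | -15 and 55 |
| 25 × 4 | 5% and 95% | -10 and 50 |
| 12 × 8 | 22% and 78% | 3 and 37 |
| 4 × 25 | 40% and 60% | 14 and 26 |

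**How often three possible readings of high variability would be met, again with no true differences:**

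| Layout | Site rates span ≥ 50 points | Some site's 95% Wilson interval excludes the pooled rate | Heterogeneity chi-square p < 0.05 |
|---|---|---|---|
| 30 × 3 | 100% | 23% | 2% |
| 25 × 4 | 100% | 73% | 3% |
| 12 × 8 | 83% | 36% | 4% |
| 4 × 25 | 0.2% | 8% | 5% |

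The readings diverge at 3 to 8 subjects per site and nearly agree at 25. Part of the 73% comes from discreteness. With no responders the Wilson upper limit is z²/(n + z²). At n = 4 this is 3.84/7.84 = 49.0%, just below 50%. At n = 3 it is 3.84/6.84 = 56.1%, which a pooled rate near 50% does not reach. The raw span, which gives the most striking column, is also the least likely choice for an analyst looking at sites of 3 or 4.

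**What depends on the classification.**

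- The primary test and its interval (SAP 7.9.1.3) use the whole Treated Analysis Set.
- The responder rates and Wilson intervals (SAP 7.9.2.4) use the same set.
- SAP 7.5 has one tested objective.
- No section lets the center review alter a model, a population or a conclusion.

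One full site carries at most 25/100 of the weight if 100 subjects are analyzed. A site whose true mean differs from the rest by 20 mm would then move the pooled mean by 0.25 × 20 = 5 mm. That bound comes from the implant ceiling and is the same whether or not a table is printed.

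**What unconditional reporting would involve.** SAP 7.2 already provides summaries "with two-sided 95% confidence intervals as appropriate", so efficacy by center is easy to produce, although SAP 7.4 imputes missing pain scores and a center table would have to say whether its values are observed or imputed. Safety is heavier. SAP 7.10 separates adverse events from device deficiencies (2), in two MedDRA layouts (2), over four phases (4): 2 × 2 × 4 = 16 tables. The subset before Month 3 adds 2 × 2 = 4, giving 20 to split over up to 30 centers if all were repeated. The noise would be considerable: 2 of 4 responders has a Wilson interval of 15% to 85%, and 4 of 8 has 21% to 79%.

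**The case for a change.** The best argument for changing the sentence is that the present rule cannot be audited. The plan names center bias as something to guard against, pools everything, and makes the one display that would show whether centers agree conditional on an unstated standard. Permission to depart from the reporting default does not supply a criterion. Printing the primary and secondary results by center, with N and an interval, would be cheap and would remove the judgment altogether.

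Much of this is true. The term is undefined, the decision does follow the results, and at small centers it could go either way. What does not follow is harm. The rule discloses when centers look discrepant, which is the finding a sponsor would have most reason to keep quiet. Selective omission therefore works against the text instead of being licensed by it. There is also partial cover elsewhere. SAP 7.4 states: "All available data will be included in the data listings and tabulations". SAP 7.10.1 puts adverse event and deficiency listings in the report, and the subject code described in Protocol 15.5 contains the site. The plan does not say that the listings carry that code, so this is help, not proof.

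**Conclusion.** The observation is accurate, but it calls for no change. SAP 7.3 leaves one word undefined in a rule about a supportive table. Followed as written, it gives the same primary estimate, p-value, responder rates and intervals whichever way the word is read, so the effect on the study's conclusions is zero. The effect on the reader is that absence of the table carries an unknown standard. That could matter if sites hold 3 to 8 subjects and matters little if they hold 25. The analysts can fill the gap when they write the report, by stating in a line how center variability was judged and what was found. Nothing in the plan prevents this.

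The spread and trigger percentages rest on equal-sized sites, a 50% responder rate, the SAP's mean of 20 mm and SD of 30 mm, and no true center differences. The conclusion that no main result is affected rests on none of these, only on the unconditional pooling in Protocol 13.1.4 and SAP 7.3.

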7.4. Handling of Missing, Unused, and Spurious Data and Dropouts

All available data will be included in the data listings and tabulations.

Imputation of values for missing pain scores for primary and secondary efficacy analyses will be performed as follows. For scheduled follow-up visits with missing VAS pain scores, if an Unscheduled Visit occurred within the scheduled visit window, and the VAS pain scores were collected at that Unscheduled Visit, the VAS pain scores from the Unscheduled Visit will be used in the analyses of that scheduled visit. Otherwise, the missing VAS pain scores will be imputed using multiple imputations (MI).

Following imputation, the objectives will be evaluated using MI analysis methods.

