## 9.19. Subject Withdrawal or Discontinuation

A subject has the right to withdraw from the study at any time and for any reason without prejudice to his/her future medical care by the principal investigator or institution. Subjects will be provided standard medical care by their physician after their study participation ends.

The study sample size accounts for expected attrition, thus subjects that discontinue after implant will not be replaced.

If a subject is withdrawn from the study, the reason for withdrawal shall be recorded on a study exit eCRF and in the subject's medical record. Examples of reasons for study discontinuation include, but are not limited to, the following:

- Eligibility criteria not met
- Pregnancy
- Failure to follow study requirements
- Subject death
- Subject lost to follow-up (LTFU)
- Subject voluntarily withdraws from the study
- Adverse events
- Normal study completion

A study exit eCRF will be completed for any enrolled subject who permanently discontinues from the study or completes the protocol-required study follow-up and has completed the study.

In the case that the subject is determined to be lost to follow-up, details of a minimum of three attempts and the method of attempt (e.g., two by phone and one by certified letter) to contact the subject must be recorded in the subject's medical records. In addition, requirements set forth by the governing IRB/EC must be followed.

The investigator should make all attempts to conduct a discontinuation visit prior to subject withdrawal if the subject is withdrawn after the Device Activation Visit and outside of a protocol-required visit. All eCRFs should be completed for visits that occurred prior to the subject’s withdrawal. In addition, regardless of when the discontinuation occurs, the subject should be asked to complete all 12-Month/Final Visit procedures, if the subject is willing, in order to obtain final assessments for the study. A study exit eCRF must also be completed.

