**Table 5. Data collection requirements for subject withdrawal**

Time of Early Withdrawal	Procedures Required
Prior to Device Activation	Complete appropriate visit eCRFs based on the visits completed (e.g. Baseline, Device Trial etc.) prior to discontinuation and the study exit eCRF.
After Device Activation and prior to the 12-Month/Final Visit	Complete all appropriate visit eCRFs based on visits completed prior to the discontinuation, the 12-Month/Final Visit eCRF (if subject is willing), and study exit eCRF.

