7.7. Treatment Characteristics

Device exposure will be quantified and summarized separately for the Trialed, Implanted, and Treated Analysis Sets. Amount of exposure will be summarized using descriptive statistics such as mean, standard deviation, sum, minimum, and maximum.

For all subjects in the Trialed Analysis Set, the number of days of device exposure will be calculated as:

$$\text{Date of trialing leads explant} - \text{Date of Trialing Day 0}$$

If the date of trialing leads explant is unavailable, and the subject discontinues from the study during the trial, study exit date will be used in place of the trialing leads explant date.

For all subjects in the Implanted Analysis Set, the number of days of device exposure between implant and device activation will be calculated as:

$$\text{Date of Device Activation Visit} - \text{Date of Implant Visit}$$

If a subject discontinues from the study after implant prior to the Device Activation Visit, the study exit date will be used in place of the Device Activation Visit date.

Months of device exposure for subjects in the Treated Analysis Set will be calculated as:

$$[(\text{Cut-Off Date} - \text{Date of Device Activation Visit})/365.25]*12$$

Where Cut-off Date for each subject is, in order of priority:

- (1) the date of permanent system explant, if applicable, or
- (2) the date of study exit, or
- (3) the most recent follow-up visit (scheduled or unscheduled).

Programming data from the Neuro Programmer Upload (NPU) database will be evaluated for subjects in the Treated Analysis Set to determine whether subjects ever received physician preference stimulation settings (ie, non-HD settings) during the study. For subjects who received physician preference stimulation settings, the months from Device Activation to first use of physician preference stimulation settings will be quantified.

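### Does the SAP need a rule for VAS scores taken at an early-withdrawal visit, and does the disagreement over the 3-month window matter?

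*SAP*

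**What the plan says.** **Missing scores.** SAP 7.4 allows one substitution before imputation. A missing scheduled VAS is replaced "if an Unscheduled Visit occurred within the scheduled visit window" and a VAS was taken there. In all other cases, "Otherwise, the missing VAS pain scores will be imputed using multiple imputations (MI"). The section gives no numeric window and does not mention discontinuation visits. It also states: "All available data will be included in the data listings and tabulations".

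**Withdrawal.** Protocol 9.19 asks the investigator to try to hold a discontinuation visit "if the subject is withdrawn after the Device Activation Visit and outside of a protocol-required visit". It adds that "regardless of when the discontinuation occurs, the subject should be asked to complete all 12-Month/Final Visit procedures", if willing. Table 5 lists the forms for a withdrawal after activation: those for visits already completed, "the 12-Month/Final Visit eCRF (if subject is willing), and study exit eCRF".

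**Visit types.** For device exposure, SAP 7.7 takes as its last fallback date "the most recent follow-up visit (scheduled or unscheduled"). Protocol 9.8 gives programming changes and adverse events as occasions for an unscheduled visit and requires a VAS at it. Withdrawal is not named.

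**Disposition.** SAP 7.1.1 tabulates the "number of subjects at these visits: Baseline, Trial Day 0, Implant, Activation, 3-Month, 6-Month, and 12-Month".

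**The 3-month window.** The synopsis gives ±15 days for Months 3, 6 and 12. Table 2 gives 90 ± 10 days for Month 3 and ±15 days for Months 6 and 12.

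**The concern.** The handling of missing scores decides which value enters the primary mean change and the three responder rates, so two competent analysts should reach the same dataset. Three things seem to stand in the way.

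- **Exit score.** A programmer who works from form labels sees a VAS on the 12-Month/Final form, finds no Unscheduled Visit form, and imputes a 3-month score although one was measured in the window. A programmer who works from dates uses the measured score.
- **Month 12.** If form name is taken as visit, a subject who leaves at three months could be counted as attending at 12 months.
- **Window.** Even under the existing Unscheduled Visit rule, two passages of the protocol put some days on opposite sides of the line. The Month 3 window, where they conflict, belongs to the primary-endpoint visit.

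A choice between these readings made after the scores are known would be open to criticism.

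**Working it through.** **The plan's own figures.** These are not in dispute.
- Primary objective: two-sided one-sample t-test, mean change 20, SD 30, alpha 0.05. The noncentral t gives n = 26 with power 0.904, which matches the stated 26. At n = 100 power exceeds 0.9999, consistent with the stated figure of over 99%.
- Secondary objectives: the Wilson 95% interval for 50/100 is 40.4% to 59.6%, a half-width of 9.6 points, as stated.

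**Windows (protocol synopsis and Table 2), with Month 3 = day 90**
- Synopsis: 90 ± 15 = days 75–105, 31 days.
- Table 2: 90 ± 10 = days 80–100, 21 days.
- Difference: days 75–79 and 101–105, 10 days.
- 12-Month Visit: 360 ± 15 = days 345–375. An exit at day 100 is 345 − 100 = 245 days before it opens.

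**Can an unscheduled VAS fall on the ten days?** Yes. Under Protocol 9.7, a subject dissatisfied with pain relief on a telephone call comes in. The 11-Week call (77 ± 3 = days 74–80) spans days 75–79, and the 3.5-Month call (105 ± 15 = days 90–120) spans days 101–105.

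**When would the disagreement change a score?** Protocol 13.3.3 and SAP 7.9.1.2 define the endpoint by the 3-Month Visit, not by a window. Protocol 9.18 treats an out-of-window visit as a deviation, and no readable text discards its score. The window therefore acts only through the substitution rule, and two things must coincide: no 3-Month VAS, and an unscheduled VAS on one of the ten days. A subject seen on days 75–79 still has all of days 80–100 ahead and must then miss the visit. A subject seen on days 101–105 who still owes the visit could complete it late.

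**When would the exit visit change a score?** Only if a subject withdraws in the 3-month window, attends an exit visit with a VAS, has no 3-Month VAS, and the analyst declines to call the visit unscheduled. Side by side, the passages point the other way:
- Protocol 9.19 places the discontinuation visit outside the protocol-required visits.
- The Schedule of Events (Table 4) has an unscheduled column and no discontinuation column.
- SAP 7.7 knows only two kinds of follow-up visit.
- The list in Protocol 9.8 is permissive, not exhaustive.

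A visit that is not scheduled is therefore unscheduled, and SAP 7.4 uses its VAS.

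**Month 12.** Table 5 also requires a study exit form. Protocol 9.19 records the reason for withdrawal on it and keeps normal completion as a separate reason, and SAP 7.7 already uses the exit date. Early exits can be identified, and SAP 7.1.1 counts subjects at visits, not forms.

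**Size per affected subject among 100**
- Responder rate: 1/100 = 1.0 point at most, and 1.0/9.6 = 10.4% of the half-width. The Wilson interval moves from 40.4–59.6% (50/100) to 41.3–60.6% (51/100).
- Mean change: 20/100 = 0.2 mm if measured and imputed scores differ by 20 mm; 100/100 = 1.0 mm at the limit of the scale. The planned SE is 30/√100 = 3.0 mm.

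**Range.** The documents give no count of such withdrawals, so these rows assume one. The mean shift assumes a 40 mm difference per affected subject.

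| Affected of 100 | Responder rate, at most | Mean shift |
|---|---|---|
| 1 | 1 point | 0.4 mm |
| 3 | 3 points | 1.2 mm |
| 5 | 5 points | 2.0 mm |
| 10 | 10 points | 4.0 mm |

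At the planned values, t = 20/3.0 = 6.7. Taking off the full 4.0 mm and holding the SD at 30 gives 16/3.0 = 5.3, still far beyond the two-sided 5% limit.

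**The case for a change.** The case for acting is that a SAP exists to remove this kind of choice. SAP 7.4 has dropouts in its title but no readable rule for a dropout's exit score. The protocol sends that score to a form named after a different visit, Table 4 gives the 12-Month/Final Visit and Unscheduled Visits separate columns, and Protocol 9.8 does not name withdrawal. Closing the gap would take a sentence and one reconciled number, with no new data. With ten affected subjects, a responder rate could move by 10 points, more than the 9.6-point half-width.

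Part of this stands. The literal reading is possible, and the synopsis and Table 2 do contradict each other. No redaction can resolve that contradiction, since both windows are visible, and the documents do not say which one governs the analysis.

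The rest is weaker. The literal reading is the least natural one. Ten affected subjects would need ten of 100 treated subjects to meet all the conditions together, and every one to change responder status. A mapping rule may also exist in blacked-out text: Protocol 13.1.2 is redacted directly after its imputation sentence, and the SAP is redacted after 7.9.1.3 and within 7.9.2.4. SAP 7.4 itself shows no redaction mark, so this is only a possibility.

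Nor is an added rule harmless. Barring every exit outside days 345–375 from Month 12 would, read literally, drop a completer whose 12-Month Visit ran late, because Protocol 9.10 makes normal completion a study exit too. Making every in-window exit VAS the efficacy score would also settle, without discussion, how to treat exits after explant or with stimulation off.

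**Conclusion.** No change to the plan follows. The treatment of the exit VAS and the Month 12 count are details left unstated that analysts can fill sensibly from the documents: an exit visit in the window is an unscheduled visit, and an early withdrawal recorded on the 12-Month/Final form is not a 12-month attendance.

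The 3-month window is a clerical inconsistency between the synopsis and Table 2. The two passages should be reconciled when the protocol is next edited. I take no view on which is intended, and no foreseeable result depends on it.

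The effect is at most 1.0 point on a responder rate and 1.0 mm on the mean per affected subject among 100. The primary conclusion does not change anywhere in the assumed range of 1 to 10 affected subjects. This rests on three assumptions: that few subjects lack a 3-Month VAS yet have a score at an in-window exit or on a disputed day, which the documents do not quantify; that out-of-window 3-Month scores are kept, since no readable text excludes them; and that the redacted text holds no contrary rule.
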